9.1.1.2 Response analysis set

All enrolled patients who are eligible, receive study treatment, have baseline assessments and at least 1 on-study tumor assessment will be considered evaluable for response. Patients who are treated and removed from study prior to on-study tumor assessment because of disease progression will be considered evaluable for efficacy and counted as failures.

9.2 Variables

9.2.1 The primary endpoints for biomarker discovery:

- 1) Level of serum miRNAs at baseline, 4 and 8 weeks of study treatment

9.2.2 The secondary endpoints are:

- 1) Eight-week clinical benefit rate (CBR), defined as proportion of patients who achieve completed response (CR) any time + partial response (PR) any time + stable disease (SD) at 8-week.
- 2) Objective response rate (ORR), will follow the RECIST criteria and will be defined as partial response (PR) or complete response (CR). Patients who are lost to follow-up without a valid response assessment will be classified as non-responders.
- 3) Progression free survival (PFS), defined as the number of days from study entry until progression or death. Patients who are alive and free from progression on the date of closing follow-up will be censored on that date.
- 4) Overall survival (OS), defined as the time in days from study entry until death. Patients who are alive on the date of closing follow-up will be censored on that date. All events of death will be included.
- 5) Safety will be assessed by determining the percent of subjects who experience unacceptable (Grade 3/4) adverse events and by describing the safety profiles. Adverse events will be summarized by the common terminology criteria for adverse events (CTCAE version 4.0).
- 6) Activation status of phosphoproteins in tissue specimens at baseline and 2-3 weeks into treatment as measured by RPMA assay.
- 7) Presence and level of mutated DNA in serum at baseline, 4 and 8 weeks of study treatment.

9.3 Statistical and analytical plans

Demographic and baseline characteristics will be summarized in all subjects using descriptive statistics.

9.3.1 Analysis for the Primary endpoints:

The analysis will be exploratory in nature. There will be no adjustment for multiplicity to be utilized.

For clinically relevant biomarker discovery, exploratory analyses of biomarkers will be performed to determine if a correlation can be established between the presence or change in the level of a marker species (“yes” or “no”) and the clinical response. Our main goal is to identify biomarkers that, when assayed at baseline, can predict the patient’s response to regorafenib. Descriptive statistics, graphical methods, and statistical modeling including repeated measure models, whichever is appropriate, may be used. The expression of biomarker levels within patients at different time points will be analyzed using paired t-test or the non-parametric Wilcoxon Signed Rank test to see whether any changes between different time points are apparent. Chi-square test or Fisher’s exact test will be used to explore the association between categorical variables and the clinical response. We may also use Cox models for association of biomarker variables (categorical or continuous) and time-to-event variables. Kaplan-Meier method will be used to explore the association between categorical variables and time-to-event response variables. ROC (Receiver Operating Characteristic) curves will also be plotted to examine the sensitivity and specificity of the identified biomarkers.

9.3.2 Analysis for the secondary endpoints:

The clinical benefit rate (CBR) will be estimated with 95% exact binomial confidence interval.

The objective response rate (ORR) will be computed for all subjects with at least one measurable lesion at baseline.

The progression free survival (PFS), as well as overall survival (OS), will be estimated and presented by the method of Kaplan and Meier (1958) and 95% confidence interval will be presented for the estimated PFS survival rate and for the median.

Safety analyses will be performed in all treated subjects. Descriptive statistics of safety will be presented using National Cancer Institute (NCI) Common Terminology Criteria for Adverse Events (CTCAE) version 4.0. All on-study AEs, treatment-related AEs, SAEs, and treatment-related SAEs will be tabulated using worst grade per NCI CTCAE v 4.0 criteria by system organ class and preferred term. On-study lab parameters including hematology, chemistry, liver function, and renal function will be summarized using worst grade NCI CTCAE v 4.0 criteria. For continuous safety variables, mean, standard deviation, and 95% confidence interval will be calculated at baseline and each visit.

Descriptive statistics (N, percentage for categorical variables and N, mean, std, median, min, max for continuous variables) will be used to summarize the activation status of phosphoproteins, presence and level of mutated DNA in serum at baseline, 4 and 8 weeks of study treatment. Repeated measures models may be used to explore the relationship between the level of mutated DNA in serum with clinical response.

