4.2 Methodology according to individual objectives

4.2.1 Primary Objective 1:

To determine the value of serum miRNA in predicting clinical benefit from regorafenib. MicroRNA (miRNA) is a new class of small, non-coding RNA that can regulate the expression of multiple genes.

miRNAs have been implicated in a diverse number of cellular processes including cell proliferation, apoptosis, regulation of embryonic stem cell development, and cancer cell invasion. Recent studies have shown that, unlike other types of biomarkers, miRNAs in the circulation are remarkably stable making them robust and reliable biomarkers of cancer. Our group has published previously on the use of miRNA to predict response to therapy (16) miRNA can be assayed in serum and therefore is an attractive new investigational tool that can prove to be very helpful. We plan to correlate the changes in serum miRNA levels with the clinical benefit of regorafenib. MicroRNA level may identify patients that are more susceptible to the beneficial effect of regorafenib. We will conduct an exploratory analysis using a panel of 380 miRNA to determine if there is a lead miRNA/s that may offer predictive value in patients who are candidates for regorafenib.

Methodology: We will use serum for miRNA quantification. 0.5 mL serum will be mixed with 10 vol of Qiazol lysis reagent and mixed by vortexing. The lysate will be extracted with CHCl_3 and the aqueous phase will be further enriched for miRNA using the miRNeasy kit (Qiagen, Valencia, CA). The miRNA-enriched fraction was eluted in RNase free water. The miRNA will be converted to cDNA using miScriptII RT kit and miRNA expression profiling will be conducted using miScript miRNA PCR arrays in combination with the miScript SYBRgreen PCR kit on an ABI 7900 HT Real-Time PCR system (Applied Biosystems, Foster City, CA). We will assay miRNA at baseline, 4 and 8 weeks. Changes in the expression between the samples will be calculated using $[\Delta][\Delta]\text{Ct}$ method with commercial software. The data will be expressed as fold up-regulation or down-regulation in miRNA expression compared to that at base level (time 0) serum sample.

4.2.2 Primary Objective 2:

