9.4 Determination of sample size

The study is exploratory in nature. The sample size is not based on certain statistical power for significance testing. However, a sample size of 40 could demonstrate an effect size of 0.5 using a 1 degree of freedom Chi-Square test with 80% power at a significance level of 5%. If the biomarkers we are looking for exhibit big changes/big-effect size, then this sample size would be sufficient for us to perform the analysis. It is estimated 40 patients will be enrolled at Georgetown University.

10. Data handling and quality assurance

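### The 380-miRNA screen has no rule for choosing leads and no false-discovery estimate, so the report would not show how many leads could be chance findings

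*Combined protocol and SAP*

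**What the plan says.** The primary objective (2.1) is to identify and rank biomarkers that later, larger trials can validate. For the miRNA part, 4.2.1 announces "an exploratory analysis using a panel of 380 miRNA to determine if there is a lead miRNA/s". The primary endpoint in 9.2.1 is "Level of serum miRNAs at baseline, 4 and 8 weeks of study treatment", and 9.3.1 gives prediction of response from the baseline assay as the main goal.

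On error control, 9.3.1 states "The analysis will be exploratory in nature" and then "There will be no adjustment for multiplicity to be utilized". It lists descriptive and graphical methods, paired tests, chi-square or Fisher's exact tests, Cox models, Kaplan-Meier curves and ROC curves. It gives no cut-off or ranking rule for leads and no q-value, permutation check or hold-out sample.

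A significance level appears only in 9.4. That section first says "The sample size is not based on certain statistical power for significance testing" and then that "a sample size of 40 could demonstrate an effect size of 0.5 using a 1 degree of freedom Chi-Square test with 80% power", at a 5% level.

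**The concern.** Screening several hundred candidates in 40 patients will produce nominal associations even if no marker predicts anything. An exploratory label justifies not controlling the family-wise error rate. It does not tell the reader how far to trust the resulting list. Setting priorities among leads is the stated objective, yet the plan says neither how a marker becomes a lead nor what share of leads should be expected to fail. Without that, a mostly sound list and a mostly false one look the same on paper, and the cost of the false leads falls on the validation studies.

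Section 9.4 adds to the difficulty. It describes 40 patients as sufficient for large effects, but the power it quotes is for one marker tested alone and says nothing about the quality of a list drawn from 380.

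**Working it through.** **Inputs.** m = 380 miRNAs (4.2.1); N = 40, effect size w = 0.5, 1-df chi-square test, 5% level, 80% power (9.4). The number of truly predictive miRNAs, m1, is not in the documents; 5, 10 and 20 are assumptions. Using 5% as a selection level is also an assumption, made because the plan gives no other level.

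**The plan's own figure.** The noncentrality is N x w² = 40 x 0.25 = 10. The two-sided 5% power of a 1-df chi-square test is then 88.5%, not 80%; N = 32 already gives 80.7%. The stated 80% is therefore conservative for a single test, and the difference does not drive this point.

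**No predictive miRNA.** Expected hits = m x 0.05 = 380 x 0.05 = 19 per contrast and outcome. Across three contrasts (for example baseline level, week-4 change and week-8 change) there are 3 x 380 = 1,140 tests and 57 expected hits.

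**Some predictive miRNAs.** Expected false hits = 0.05 x (380 - m1). Expected true hits = power x m1. Share false = false / (false + true).

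| m1 | False hits | True hits (88.5% power) | Share false | Share false at the stated 80% power |
|---|---|---|---|---|
| 5 | 18.75 | 4.43 | 81% | 82% |
| 10 | 18.5 | 8.85 | 68% | 70% |
| 20 | 18.0 | 17.71 | 50% | 53% |
| 38 | 17.1 | 33.64 | 34% | 36% |

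**Break-even.** Half the hits are false when m1 = 380 x 0.05 / (0.05 + power). This gives 19 / 0.935 = 20.3 at 88.5% power and 19 / 0.85 = 22.4 at 80%.

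**If Fisher's exact test is used.** With a 20/20 marker split and 44% clinical benefit (the disease control rate quoted in 1.2.2), the actual size is about 2.2%. Power for 25% versus 75%, which is w = 0.5 at that split, is about 83%. Expected chance hits fall to 380 x 0.0219 = 8.3. The false share for 5, 10 and 20 predictive markers becomes 66%, 49% and 32%, and break-even is at about 10 markers.

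**What stricter rules would cost.** Bonferroni (0.05 / 380 = 0.00013) leaves 25% power at N = 40 and needs N = 88 for 80%. A fixed Benjamini-Hochberg cut-off of q < 0.20 (simulation, independent tests, m1 = 5 / 10 / 20) holds the false share at about 19-20%. It reduces true leads from 4.4 / 8.8 / 17.7 to 2.7 / 6.2 / 14.3, a loss of about 39%, 30% and 19%.

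**Correlation.** The expected count of 19 does not depend on independence, but its spread does. With all markers null, the 5th-95th percentile range of chance hits is 12-26 under independence and 5-57 under an assumed common correlation of 0.3.

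**The case against.** The strongest reply is that the omission is disclosed and conventional. The analysis is labelled exploratory, the sample size is expressly not power-based, and false leads are meant to be filtered out by later validation. Missing a true marker at this stage may cost more than carrying a false one, so a strict threshold would be the wrong remedy. All of this stands. It answers a demand for family-wise control or a fixed cut-off, but not the absence of any description of how reliable the list is.

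Several stronger readings are tempting, and the documents do not support them:

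- A reader might infer that leads will be called at p < 0.05. Nothing in the plan says so. The 5% in 9.4 is a yardstick for one test, and the gap is that no rule exists.
- A reader might infer that most leads would be chance findings. That depends on how many miRNAs are truly predictive, which is not stated. Looking for a lead miRNA or miRNAs suggests that few are expected, but fixes no number.
- A reader might infer that the plan forbids a false-discovery estimate. It declines adjustment; it does not bar reporting q-values or the number of tests. A reader could also compare the hits with 19, although correlation makes that comparison unreliable, and q-values need all 380 p-values, which the plan does not promise to publish.
- A reader might extend the sentence to the 100-125 proteins. It sits under the primary endpoints, and 9.2.1 lists only miRNA there. The phosphoproteins are a secondary endpoint in 9.2.2, with separate analysis text in 4.2.2 and 9.3.2.

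**Conclusion.** The point holds in a limited form. The plan screens 380 miRNAs for leads, declines multiplicity adjustment, and provides neither a selection rule nor a false-discovery estimate. If 5% were used, about 19 chance hits per contrast would be expected under the global null. The false share would be about 81%, 68% or 50% with 5, 10 or 20 truly predictive miRNAs. These shares assume w = 0.5 for every true marker, all 40 patients evaluable and tests of nominal size; they are ratios of expected counts.

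A false majority is therefore possible but not established. It requires fewer than about 20-22 predictive miRNAs, or about 10 with Fisher's exact test. The weakness is in how the results can be interpreted. It does not invalidate the study or its decision to forgo family-wise control.

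**What to change.** Keep the exploratory label and replace the multiplicity sentence in 9.3.1 with wording such as:

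> No family-wise adjustment will be made. Unadjusted p-values will be reported for all miRNAs tested, together with Benjamini-Hochberg q-values computed within each contrast and outcome, the number of markers tested and the number of hits expected by chance.

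Use the q-values to describe how reliable the lead list is. A mandatory cut-off such as q < 0.20 is not needed, given the true leads it would drop. Within one contrast and outcome the q-values keep the order of the p-values, so the ranking there does not change. In 9.4, add that the quoted power applies to one marker tested alone.

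The cost is two short text changes and one extra table column, with no additional patients, samples or assays. The downside is that some leads will look less convincing than their unadjusted p-values suggest.

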1.2.2 Clinical experience

Two phase III global randomized studies have evaluated the efficacy of regorafenib. The CORRECT (Patients with metastatic colorectal cancer treated with regorafenib or placebo after failure of standard therapy) trial is an international, multicenter, randomized, double-blind, placebo-controlled study that enrolled 760 patients with mCRC whose disease has progressed after approved standard therapies. Metastatic colorectal cancer patients were randomized to regorafenib plus best supportive care (BSC) or placebo plus BSC. Treatment cycles consisted of 160 mg of regorafenib (or matching placebo) once daily for three weeks on / one week off plus BSC. The primary endpoint of this trial was overall survival. Secondary endpoints included progression-free

survival, objective tumor response rate and disease control rate. The safety and tolerability of the two treatment groups were also compared.

At a preplanned second interim analysis, there was a statistically significant survival benefit for regorafenib. The estimated hazard ratio for overall survival was 0.773 (95% confidence interval [CI], 0.635 to 0.941; 1-sided $p = .0051$). Patients treated with regorafenib had a median overall survival of 6.4 months, compared with 5.0 months for placebo — a 29% increase in survival. In addition to improved overall survival, progression-free survival was superior; median progression-free survival was 1.9 months (95% CI, 1.88 to 2.17) for regorafenib and 1.7 months (95% CI, 1.68 to 1.74) for placebo. The estimated hazard ratio for progression-free survival was 0.493 (95% CI, 0.418 to 0.581; 1-sided $p < .000001$). There was a substantial difference in disease control rate in the regorafenib and placebo groups (44% vs. 15%; $p < .000001$). Regorafenib demonstrated comparable efficacy benefits across patient subgroups analyzed including age, number of metastases, number of lines of prior therapy, and *kras* status.

The most frequent grade 3+ adverse events in the regorafenib group were hand–foot skin reaction (17%), fatigue (15%), diarrhea (8%), hyperbilirubinemia (8%), and hypertension (7%). The efficacy and safety from the CORRECT study supported FDA approval in September 2012.

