The efficacy and safety of regorafenib were examined in the Phase III GRID trial in patients with gastrointestinal stromal tumors (GISTs) who had exhausted all other treatment options. The study involved 199 patients with metastatic and/or unresectable GIST that had become resistant to imatinib and sunitinib. Patients were randomized 2:1 to regorafenib (160 mg orally once daily on a 3 weeks on/1 week off cycle) or placebo, plus best supportive care.

The results showed that treatment with regorafenib led to a statistically significant 3.9-month improvement in progression-free survival (PFS), compared with placebo (4.8 months vs. 0.9 months; hazard ratio [HR] = 0.27; $p < .0001$). Overall survival was statistically similar between groups as expected due to a trial design that allowed crossover to regorafenib for disease progression (85% for placebo and 31% regorafenib randomized patients). The median survival period without tumor growth among patients on regorafenib was 4.8 months while for the control group on placebo it was less than a month. The overall disease control rate combining partial responses with durable stable disease for at least 12 weeks was 53% with regorafenib compared with 9% in the control group. The most common grade ≥ 3 adverse events associated with regorafenib were hand–foot skin reaction (56.1%), hypertension (48.5%), and diarrhea (40.9%). The efficacy and safety of the GRID study data supported FDA approval February 2013.

2. Study objectives

2.1 Primary objective:

To prospectively identify and prioritize leading biomarkers in tumor tissue and/or serum that are potentially predictive of response to regorafenib in patients with metastatic colorectal cancer, and can be further validated in subsequent larger clinical trials.

2.2 Secondary objective:

To prospectively determine the molecular mechanisms by which regorafenib can control colorectal tumors refractory to other treatments.

3. Investigator[s] and other study participants

Principal Investigator

[name] MD

[name]

[name]

Email: [contact]

Co-Principal Investigators:

[name] [name]

[name]

[name]

Email: [contact]

[contact]

[name] [name]

[name]

[name]

Email: [contact]

[contact]

[name] [name]

[name]

[name]

Email: [contact]

[contact]

[name] PhD

George Mason University

[name]

[name]

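### ROC sensitivity and specificity for miRNAs picked from 380 are taken from the same 40 or fewer patients, with no correction for the picking

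*Combined protocol and SAP*

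**What the plan says.** The primary objective (Section 2.1) is "To prospectively identify and prioritize leading biomarkers in tumor tissue and/or serum that are potentially predictive of response to regorafenib", with validation left to later, larger trials. Section 4.2.1 describes an exploratory analysis "using a panel of 380 miRNA to determine if there is a lead miRNA/s" of predictive value. Section 9.3.1 states the aim: "Our main goal is to identify biomarkers that, when assayed at baseline, can predict" response. It calls the analysis exploratory and says "There will be no adjustment for multiplicity to be utilized". It lists association tests and models, then adds that ROC "curves will also be plotted to examine the sensitivity and specificity of the identified biomarkers".

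The data are one uncontrolled cohort of 40. Section 9.1.1.2 says that patients who are eligible, are treated and "have baseline assessments and at least 1 on-study tumor assessment will be considered evaluable for response". The plan does not state:
- what makes a miRNA count as identified;
- how a cut-off is chosen;
- which binary outcome the ROC uses (4.2.1 speaks of clinical benefit, 9.3.1 of clinical response);
- any hold-out set, cross-validation or bootstrap.

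On sample size, Section 9.4 says that N is not power-based, then that "a sample size of 40 could demonstrate an effect size of 0.5 using a 1 degree of freedom Chi-Square test with 80% power" at the 5% level.

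**The concern.** A marker chosen because it separates responders from non-responders in these patients will look accurate in these patients, whether or not it is. With 380 candidates and about 40 patients that optimism is large. It is separate from the declared absence of multiplicity adjustment: that concerns p-values, whereas this concerns the sensitivity, specificity and AUC that would be reported.

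The study exists to rank leads for further work, and ROC is the only measure of predictive accuracy that 9.3.1 names. A reader shown sensitivity and specificity above 70% for a lead would not know that a panel with no predictive value would show much the same.

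**Working it through.** **1. The plan's own figure (9.4).** Inputs: n = 40, effect size 0.5 (unlabelled; read as Cohen's w because it is tied to a chi-square test), 1 df, 5%.
- Noncentrality = n × w² = 40 × 0.25 = 10.
- Power ≈ Φ(√10 − 1.96) = Φ(3.162 − 1.960) = Φ(1.202) = 0.885. The stated 80% is not reproduced.
- n = 32 gives Φ(√8 − 1.96) = Φ(0.868) = 0.807.
- At n = 40, 80% power corresponds to w = (1.960 + 0.842)/√40 = 0.443.
- Possible unstated explanations: 32/0.80 = 40 (20% not evaluable), or a continuity correction (19 per group, 38 in total, for 25% versus 75%). Exact power for 20 versus 20 at 25% versus 75% is 83% with Fisher's test and 82% with the Yates correction.
- The figure describes one marker tested once.

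**2. Inputs for the selection effect.** 380 miRNAs (4.2.1) and 40 patients. The responder share is an assumption, taken from Section 1.2.2: "There was a substantial difference in disease control rate in the regorafenib and placebo groups (44% vs. 15"%). That trial used a different dose. 0.44 × 40 = 17.6, so 18 versus 22. Two alternatives were tried: 32 evaluable (0.44 × 32 = 14.1, so 14 versus 18) and 10 versus 30. Between-marker correlation ρ is not in the documents, so 0, 0.3 and 0.6 were used. Because the plan gives no selection rule, two were assumed: keep every miRNA with two-sided Wilcoxon p<0.05, or keep the best one.

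**3. Smallest AUC that passes p<0.05, 18 versus 22.** Null SD of the AUC = √[(n+1)/(12·n₁·n₀)] = √[41/(12 × 18 × 22)] = 0.0929. Threshold = 0.5 + 1.96 × 0.0929 = 0.682. The AUC moves in steps of 1/396, so the first value above it is 271/396 = 0.684. Under this rule no kept marker can show less, whatever its true value.

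**4. Null simulation** (no miRNA has any value; AUC taken in whichever direction exceeds 0.5; 1,500 runs per setting). Mean apparent AUC at ρ = 0 / 0.3 / 0.6:

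| Split | Best of 380 | Kept at p<0.05 |
|---|---|---|
| 18 vs 22 | 0.784 / 0.767 / 0.731 | 0.716 / 0.716 / 0.717 |
| 14 vs 18 | 0.818 / 0.801 / 0.763 | 0.741 / 0.741 / 0.742 |
| 10 vs 30 | 0.823 / 0.805 / 0.767 | 0.746 / 0.746 / 0.747 |

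About 380 × 0.05 = 19 miRNAs per comparison would pass p<0.05 by chance. At the Youden cut-off, 18 versus 22, the p<0.05 rule shows sensitivity 73% and specificity 71%. The best of 380 shows 74 to 78% and 72 to 75%. With no predictive value the two should sum to 100%.

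**5. How much is selection.** One pre-specified null marker, with direction and cut-off still read from the data, shows a median AUC of 0.56 and sensitivity + specificity = 0.64 + 0.61 = 1.25. The best of 380 independent markers shows a median AUC of 0.78 and 0.78 + 0.75 = 1.53.

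**6. What a correction returns, 18 versus 22, no marker working.** Five-fold cross-validation with the marker re-picked in each training set gives AUC 0.49 to 0.50 (SD 0.10 to 0.12). With the cut-off also re-picked, sensitivity + specificity is 0.99 to 1.00. Bootstrap optimism correction with selection repeated gives 0.58 to 0.61.

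**7. When one real marker is present.** A miRNA with true AUC 0.85 ranks first on apparent AUC in 85 to 92% of runs (ρ 0 to 0.6). At 0.80 it does so in 62 to 82%, and at 0.75 in 32 to 63%. For the 0.85 case at ρ = 0.3, mean apparent AUC is 0.86 and cross-validated AUC is 0.76 (SD 0.15).

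**The case against.** The plan is candid. It calls the work exploratory, waives multiplicity adjustment, sends leads to later trials, and only plots ROC curves without promising unbiased accuracy or a go/no-go rule. All of that stands, and it protects the final claims. It does not tell a reader that the plotted figures carry selection bias, nor does it remove that bias.

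A reader might infer that the curves are useless for ranking. The documents do not support that: 9.4 ties its statement of adequacy to large effects, and a strong marker does usually rank first (step 7). The difficulty lies with weak and moderate markers.

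A reader might also take the cohort to shrink through early progression. Section 9.1.1.2 goes on to count patients removed for progression before an on-study assessment as failures, 8.2.2 counts those lost without a valid assessment as non-responders for ORR, and 5.2.3 replaces withdrawals before the first biopsy. Some loss remains possible, but its size is unknown.

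The case against cross-validation has force. With selection repeated, it scores the selection procedure and not a named miRNA: at ρ = 0.3, 20 training sets picked on average 9 different miRNAs when none worked, and 3 to 4 when one had AUC 0.85. It is pessimistic for that real marker, and 18% of such studies would report below 0.60. The bootstrap gave a similar mean there (0.75 against 0.77 in the same runs) with less noise (SD 0.09 against 0.15). If response means CR or PR, there may be too few responders for five folds. These points shape the remedy. They do not make the uncorrected figure adequate.

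Finally, the 0.684 floor follows from an assumed Wilcoxon screen that 9.3.1 does not name for this comparison. The best-of-380 figures do not depend on that screen.

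**Conclusion.** The concern holds. The planned ROC figures are optimistic by construction. With no true signal and an 18 versus 22 split, apparent AUC would be about 0.72 for markers kept at p<0.05 and 0.73 to 0.78 for the best of 380, against a true 0.50. Smaller or less balanced samples raise this to about 0.74 to 0.75 and 0.76 to 0.82. Apparent accuracy in this range does not distinguish a weak or moderate lead from chance.

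The size rests on the borrowed responder share, the assumed correlations and the two assumed selection rules. The direction does not: the bias appears in every setting tried.

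The documents do not support reading this as a fault in the declared multiplicity waiver, as a statement that ROC results decide which leads advance, or as a shortage of patients. The 9.4 slip is a conservative reporting error on a sample size that the plan says is not power-based.

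**What to change.** In 9.3.1:
- Before analysis, state the rule that makes a miRNA identified, the cut-off rule and the binary outcome. If the outcome is clinical benefit, first reconcile 8.2.1 (stable disease at 8 weeks) with 8.3.6.5 (stable disease of at least 8 weeks).
- Label the plain ROC curves, and the sensitivity and specificity read from them, as apparent and uncorrected for selection.
- Beside them, report AUC, sensitivity and specificity from stratified repeated cross-validation, with marker and cut-off picked again inside every resample and the number of folds set by the smaller outcome group. Describe this as the performance of the selection procedure, not of a named miRNA.
- Show the permutation (null) distribution of the best apparent AUC as the benchmark for each lead. In the simulated 18 versus 22 setting its 5th to 95th percentile range was 0.74 to 0.84 for independent markers and 0.69 to 0.82 at ρ = 0.5.
- Bootstrap optimism correction may be added, noting that in these simulations it stayed at about 0.58 to 0.61 when no marker worked.

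In 9.4 (minor): restate as 88.5% power at w = 0.5, or 80% at w = 0.44, or give the evaluability allowance or continuity correction behind the 80%. Add that the figure is for one marker tested once.

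Cost: wording and modest code, with no change in N. Section 4.1 defers blood analysis until the last sample is in, so the plan leaves room to set these rules first. The price is that the corrected figures are imprecise (SD 0.10 to 0.15) and pessimistic for a real marker (0.76 when the true AUC is 0.85).
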